7.4 Follow-up

If an adverse event/experience occurs, the subject under the direction of the Investigator (or designee) may be referred to the nearest acute care facility for treatment. Serious or Unexpected Drug Event/Experience will be followed to resolution or until the AE has stabilized. Any adverse event will be documented on an Adverse Event Report and entered on the eCRF.

Page 29 of 53 Zurex Pharma, Inc. Project: ZX-ZP-0092 Microbac Protocol: 865.1.03.25.18

Microbac Project: 865-107

8. Statistics

8.1 Data Sets Analyzed

The Intent-to-Treat (ITT) population will consist of all subjects who pass the pre-test period prior to baseline screening and are assigned a subject number for treatment. The ITT data set will include data for all of the ITT population. The ITT data set will be used for the safety analysis.

[figure not shown]
Since each body site (left or right for abdomen or groin) can pass or fail Treatment Day baseline requirements separately, the per-protocol data set will be defined as those sites passing treatment day baselines on a site-by-site basis. Subjects are therefore included in the per-protocol population if and only if they have at least one qualifying body site. The per-protocol data set will be evaluated for efficacy.

8.2 Statistical Methods

8.2.1 Efficacy Analyses

CFU values will be calculated as per the Bacterial Enumeration methods above. Individual plate CFU counts that are zero will be treated as 0.5 for further calculations.

Product effectiveness will be measured using superiority and non-inferiority estimates for the 30-second sample time calculated using average treatment effects (ATEs). ATEs will be estimated from a linear regression of the 30 second post-treatment bacterial counts (\log_{10} scale) on the additive effect of a treatment indicator and the baseline or pre-treatment measurements (\log_{10} scale). Superiority and non-inferiority will be estimated as follows:

Superiority and non-inferiority will be calculated separately for each body area.

Persistence or long-term efficacy is defined as having the 6 hours post-

Page 30 of 53 Zurex Pharma, Inc. Project: ZX-ZP-0092 Microbac Protocol: 865.1.03.25.18

Microbac Project: 865-107

treatment log₁₀ CFU/cm² values lower than or equal to the baseline log₁₀ CFU/cm² values for 100% of the subjects in each body area. Due to the normal variability associated with this biological system, the test article is considered to have persistent effect if the percentage of body sites with log₁₀ CFU/cm² values less than or equal to baseline for the 6-hour sample is between 95 to 100%. All subjects that do not achieve the 6-hour efficacy goal will be documented and discussed.

The efficacy calculations (superiority and persistence) only apply to ZuraPrep $^{\text{TM}}$ for the purpose of determining efficacy, but the same calculations will be performed for ChloraPrep $^{\text{R}}$ for information purposes only.

Summary statistics for the log₁₀ CFU/cm² values at each time point and the respective changes from baseline will be calculated, grouped by time point, test product, and body area. These statistics are for information purposes only and are not part of efficacy calculations.

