3.1 Study Type

This is a randomized, paired-comparisons design where each subject receives two of the planned treatments.

 Table 3.1:
 Treatments, Anatomical Sites of Evaluation, Application and Dry Times and Coverage

Areas (See Appendix 14.7 for detailed application instructions)

Treatment (Quantity/Volume)	Body Site	Application Time	Dry Time	Area of Coverage
ZuraPrep™	Abdomen (sebaceous poor)	30 seconds	3 minutes	5" x 5"
	Groin (sebaceous rich)	2 minutes	3 minutes	1.5" x 5"
ChloraPrep®	Abdomen (sebaceous poor)	30 seconds	3 minutes	5" x 5"
(active control)	Groin (sebaceous rich)	2 minutes	3 minutes	1.5" x 5"
ZuraPrep™ Vehicle,	Abdomen (sebaceous poor)	30seconds	3 minutes	5" x 5"
(negative control)	Groin (sebaceous rich)	2 minutes	3 minutes	1.5" x 5"

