3.3 Randomization and Blinding

Subjects will be randomized before treatment, after screening eligibility is determined. Subjects will be randomized to treatment using the following block design:

Treatment Balance

Each subject will receive two different treatments, one on the right side of the body and one on the left.

The treatment assignments will be balanced such that the number of readings per anatomical site matches the calculated requirements.

Page 9 of 53 Zurex Pharma, Inc. Project: ZX-ZP-0092 Microbac Protocol: 865.1.03.25.18

Microbac Project: 865-107

Left/Right Balance

The application will be randomized so that each treatment is used on an equal number of left and right sides of the body.

Site and Sample Time Balance

Within each anatomical site, sample order with respect to sampling area number will be balanced with respect to treatments.

The randomization plan is based on the estimated population size

Subjects will be randomized to treatments in blocks of 12, randomly ordered within the block. Sample order will be randomized separately in blocks of 24 based on the 24 possible sample orders; 12 of the sample orders will be matched to the 12 treatment assignments in such a way to balance treatment with respect to sample order. Additional details on the randomization will be found in the randomization document.

The Investigator is responsible for ensuring that the randomization is followed. A basic outline of a randomization schedule for the abdominal and groin sites is provided in Appendix 14.4. The final randomization schedule will be prepared before the initial treatment. The test and control articles will be labeled with the appropriate codes as designated by the study randomization.

Subjects will be identified by their initials, a Screening ID Number, and a Subject Number. Subject Numbers will not be assigned until a subject has passed the screening criteria, including baseline bacterial counts (at least 1.0×10^5 CFU/cm² in the groin and at least 1.0×10^3 CFU/cm² on the abdomen). Subjects whose abdominal and groin regions qualify will be assigned the Subject Number on Treatment Day. Therefore, each of the participating treated subjects will be assigned two identification numbers: Screening Identification Number and a Subject Number.

- Screening subjects will be assigned numbers ranging from 9001 to 9999.

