4.1 Subject Inclusion Criteria

Subjects to whom all of these conditions apply will be eligible for enrollment in this study:

- Healthy male and female volunteers, 18 years of age or older.
- Are in good general health.
- Be able to present a valid identification card that includes name and date of birth.
- Have skin within 6 inches of the test sites that is free of tattoos, dermatoses, abrasions, cuts, lesions or other skin disorders.
- Willing to avoid antihistamines, immunosuppressants, or oral steroids for the duration of the study. (other than hormones for contraception or post-menopausal reasons).
- Wiling to avoid topical or systemic antimicrobial exposure for the duration of the study. Restrictions include, but are not limited to antimicrobial soaps,

Page 17 of 53 Zurex Pharma, Inc. Project: ZX-ZP-0092 Microbac Protocol: 865.1.03.25.18

Microbac Project: 865-107

antiperspirants/deodorants, shampoos, lotions, perfumes, after shaves, colognes, and topical or systemic antibiotics.

- Cooperative and willing to follow Subject Instructions (Appendix 14.6).
- Cooperative and willing to sign Consent Form / HIPAA Authorization Form.
- Have Screening Day baseline counts of at least 1.0 x 10³ CFU/cm² per abdominal site (left and right) and at least 1.0 x 10⁵ CFU/cm² per groin site (left and right).

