5.1.1.2 Screening Day (Qualification Baseline Sampling)

Subjects will be required to refrain from bathing or showering 72 hours prior to Treatment Day and hair will be clipped at least 48 hours prior to Screening Day.

After the washout period and at least 3-days before Treatment Day, the Investigator or a designated assistant will complete the Screening Day Inclusion/Exclusion Criteria data capture form.

Prior to performing the Screening Day baseline sample collection, a skin irritation assessment will be performed

If an irritation score of 1 for any individual skin condition at the Screening Day baseline is assigned, the subject will be excluded from the study.

A baseline screening sample will be collected from each test area using the Williamson-Kligman scrub cup technique³. Baseline samples will be taken from the center of each contra lateral test area within each anatomical region. Samples from both the left and right sides of a body region must meet the minimum value indicated in the Inclusion Criteria for the subject to be enrolled into the treatment phase of the study for that region. Subjects must qualify for both the abdominal portion and the groin portion of the study.

Subjects who qualify for the study will be notified and will continue to follow the subject instructions until completion of the scheduled Treatment Day.

Subjects will again be required to refrain from bathing or showering 72 hours prior to Treatment Day and hair will be clipped at least 48 hours prior to Treatment Day.

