6.1 Efficacy Parameters

The primary measure of antimicrobial efficacy is the reduction of skin flora on the abdominal and groin sites 30 seconds following application of the study treatments relative to the Treatment Day baseline counts.

Product effectiveness will be measured using superiority and non-inferiority estimates for the 30-second sample time calculated using Average Treatment Effects (ATEs). The ATE will be estimated from a linear regression of the 30-second post-treatment bacterial count (log₁₀ scale) on the additive effect of a treatment indicator and the baseline or pre-treatment measurements (log₁₀ scale). To show effectiveness the test product will be 1) non-inferior to ChloraPrep® with a 0.5 margin (upper bound of 95% confidence interval of the ATE of the test product versus active control value < 0.5) and (2) superior to the ZuraPrep Vehicle (negative control) by a margin of 1.2 (lower bound of 95% confidence interval of the ATE of the test product versus the vehicle value > 1.2). Superiority and non-inferiority will be calculated separately for each body area (abdomen and groin).

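### The primary regression leaves out body side, sampling site and the Screening Day count, so its confidence intervals may be wider than necessary; adding these terms is a cheap improvement

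*Combined protocol and SAP*

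**What the plan says.** - **Model.** Sections 3.2, 6.1 and 8.2.1 describe the same regression, fitted separately by body area: the 30-second log10 count "on the additive effect of a treatment indicator and the baseline or pre-treatment measurements". Side, sampling site and a separate Screening Day term are not named.
- **Which baseline.** The model sentence does not say. Section 6.1 defines the efficacy measure "relative to the Treatment Day baseline counts", which points to the Treatment Day count.
- **Balance by design (Section 3.3).** "The application will be randomized so that each treatment is used on an equal number of left and right sides of the body". Also: "Within each anatomical site, sample order with respect to sampling area number will be balanced with respect to treatments".
- **Screening Day count.** Section 5.1.1.2: "A baseline screening sample will be collected from each test area". Its only stated use is as an eligibility threshold in Section 4.1: "Have Screening Day baseline counts of at least 1.0 x 10³ CFU/cm² per abdominal site (left and right"), with a corresponding minimum for the groin.
- **Decision rules.** Non-inferiority to the active control requires the upper 95% bound to lie below 0.5. Superiority over vehicle requires the lower 95% bound to lie above 1.2.

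**The concern.** Balancing a factor that predicts the outcome and then omitting it from the model leaves its variance in the residual. The model-based standard error is then larger than it should be. The Treatment Day baseline cannot absorb a position effect, because Sections 5.1.2.1.1 and 5.1.2.1.2 take the baseline and the 30-second sample from different numbered sites.

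The design balance may also not carry through to the analysis set. Sites leave the per-protocol set one by one on their Treatment Day counts (Table 3.2, Section 8.1). Covariates would adjust for whatever imbalance results.

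The Screening Day count is a second pre-treatment measure of the same test area, and it is already collected. Each area thus has two pre-treatment counts, and the model sentence leaves open which one enters.

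Both primary claims rest on confidence bounds, so needless width costs power. Terms added after the data are seen would be a deviation to be justified under Section 8.6.

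**Working it through.** **The plan's own figures.** 108 subjects × 2 sides / 3 treatments = 72 readings per treatment, which matches Table 1.5. The 65 per treatment in Section 8.3 cannot be checked, because its SD and expected effect are not visible. Assuming a two-sided 95% interval, 80% power and a true difference of 0, it implies for non-inferiority

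SD = 0.5 × √(65/2) / (1.960 + 0.842) = 1.017.

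At 72 per treatment, SE = 1.017 × √(2/72) = 0.16957. The CI half-width is 1.96 × 0.16957 = 0.332. Power is Φ(0.5/0.16957 − 1.96) = 83.9%.

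**Side and site, each alone (total SD 1.017).**
- A left/right mean difference d contributes variance d²/4. The cut is 1 − √(1 − (d²/4)/1.017²): 0.5% at d = 0.2 and 3.1% at d = 0.5.
- A site-position SD s contributes s². The cut is 1 − √(1 − s²/1.017²): 0.5% at s = 0.1, 2.0% at 0.2 and 4.4% at 0.3.

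**Non-inferiority against superiority.** Assume residual SDs of 0.95 for the two active products and 0.5 for vehicle, each comparison fitted on its two treatments, and ignore the remaining subject variance.
- Non-inferiority: residual variance 0.95² = 0.9025. The cut is 1 − √(0.9025/0.9425) = 2.1% at s = 0.2, and 1 − √(0.9025/0.9925) = 4.6% at s = 0.3.
- Superiority: average residual variance (0.9025 + 0.25)/2 = 0.576. The cut is 1 − √(0.576/0.616) = 3.3% at s = 0.2, and 1 − √(0.576/0.666) = 7.0% at s = 0.3.

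Simulations of the bilateral block-of-12 design with assumed SDs agree. Side plus site cuts the SE by about 2% to 5% (non-inferiority) and 3% to 7% (superiority) at s = 0.2 to 0.3. The extended models cover at 94% to 96%. With no side or site effect the SE is 0.5% to 0.7% larger.

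**Screening Day count.** The gain depends on its correlation with the outcome given the Treatment Day baseline, which the documents do not state. In simulation it was roughly 0% to 2%.

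**All added terms together.** For joint partial correlation r the cut is 1 − √(1 − r²): 0.5%, 2.0% and 4.6% at r = 0.1, 0.2 and 0.3.

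**Power for non-inferiority.** Φ(0.5/(0.16957 × (1 − x)) − 1.96) gives 85.3% for a cut of x = 2% and 87.4% for x = 5%, against 83.9% with no cut.

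**The case against.** **No effect is documented.** No side difference, position SD or screening correlation appears anywhere. A reader might infer that the intervals are certainly too wide; the documents do not support that. With no prognostic value there is nothing to gain. This stands, and every size above is conditional on it.

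**Nothing is invalid.** A reader might also infer a biased estimate or an inflated error rate. Neither follows: leaving out a balanced factor makes the interval at most conservative. While balance holds, the estimate itself barely moves; in balanced simulations its actual spread changed by under 0.3%. The gain comes from a reported SE closer to that spread. This stands.

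**Balance and block size.** Sample orders come in blocks of 24 and 108/24 = 4.5, so a reader might infer that balance fails by design. It does not follow. Section 3.3 matches 12 sample orders to each 12 treatment assignments. A block of 12 gives 12 × 2/3 = 8 readings per treatment, or 2 at each of four sites, and 108/12 = 9 whole blocks. Loss of sites from the per-protocol set is the valid reason that balance may be lost.

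**Power is already adequate.** The plan has 72 sites per treatment against 65 required, and replaces non-qualifying sites. This stands, and limits the point to an improvement.

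**Pairing matters more.** Section 3.1 states: "This is a randomized, paired-comparisons design where each subject receives two of the planned treatments". Modelling that pairing would narrow the interval by 6.6%, 16.3% or 29.8% at an assumed within-subject correlation of 0.2, 0.4 or 0.6. Appendix 14.4 also suggests one sample order per subject, so position would largely cancel within a subject and the site term would gain less in a paired model. This stands as a separate point; it does not make the covariates wrong in the model as written.

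**Unseen text.** The estimation detail that Section 8.2.1 introduces is absent from the public copy, as is the randomization document. The statement is therefore about the visible model. Sections 3.2 and 6.1 repeat it with the decision rules and add no term.

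**Conclusion.** The point holds as a conditional one about precision. The visible primary model omits two factors that the design balances on and a pre-treatment count that is collected on every test area. If they are prognostic beyond the Treatment Day baseline, the primary intervals are wider than necessary.

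At an assumed site-position SD of 0.2 to 0.3 log10, most of the gain comes from site number; side adds little unless the left/right difference is large. The Screening Day count is the weakest of the three: it is taken at least 72 hours before treatment and is truncated from below by eligibility. The power figures rest on an SD solved back from 65 under a true difference of zero. The case for acting is the asymmetry between a plausible gain of a few percent and a loss of under 1%. This is a cheap improvement, not the correction of an error.

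**What to change.** In Sections 3.2, 6.1 and 8.2.1, before any outcome data are seen:

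1. State that the baseline covariate is the Treatment Day log10 CFU/cm² of the same test area.
2. Prespecify body side and the sampling-site number of the 30-second sample as covariates.
3. Add the Screening Day log10 CFU/cm² of the same test area as a further covariate.
4. Keep the unextended model as a sensitivity analysis.

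The cost is wording and five degrees of freedom (1 for side, 3 for site, 1 for the Screening Day count), with no new samples or visits. The downside is intervals under 1% wider if none of the factors has an effect. Section 3.2 ties the primary analysis to the Final Rule, so the sponsor should confirm that the added covariates fit that standard. The handling of within-subject pairing should be settled at the same time, as its own item.

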8.2.2 Safety Analysis

The ITT population will be analyzed for safety. Skin irritation scores assessed in accordance with Appendix 14.11 will be reported for any subject who is scored with a 1 or more at any observation [baseline (screening day and treatment day), post-application/prior to 30 second and 6 hour sampling procedures], in any category for any site.

Adverse events (including post-treatment skin irritation scores of 3 in accordance with Appendix 14.11, will be summarized. Summary tables will present incidence rates of adverse events by treatment group for all subjects who enter the treatment period. Listings of adverse events will be provided.

The statistical significance of differences in skin irritation between the three treatments will be evaluated using Fisher's exact test on skin irritation data summarized as follows: any reaction above zero (no reaction) on the skin irritation rating scale for any category (erythema, edema, rash, and dryness) for any post-treatment sampling time will be considered a positive signal for that substance. If Fisher's exact test shows statistically significant skin irritation between the three treatments, a secondary analysis will be conducted to determine how the reactions differ.

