7.1 Safety Parameters

The principal measures of safety will be the recording of skin irritation scores and the incidence of adverse events reported during the study.

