7.2 Assessment Methods for Skin Irritation

After the washout period, the Investigator or designated sub-investigators trained by the Investigator will assess the subject's skin condition and assign a skin irritation rating score using the Skin Irritation Rating Scale (see Appendix 14.11). A skin irritation score will be recorded at both the screening and treatment phases prior to baseline sample collections and prior to each post-treatment application sample collection (30 seconds, and 6 hours).

A corresponding rating score for each individual skin condition, for each site will be recorded on the appropriate data capture form and entered in the subject's eCRF. (See Appendix 14.11, which includes the following four independent evaluation categories: Erythema, Edema, Rash, and Dryness).

If an irritation score of 1 or greater for any individual skin condition prior to the baseline sample collection (at either the screening or treatment day phases) is assigned, the subject will be excluded from the study (no study treatment will be applied).

If an irritation score of 3 for any individual skin condition at any observation period is assigned, the subject will be discontinued from the study and an adverse event will be recorded. See Section 7.3 (Adverse Events).

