14.11 Skin Irritation Rating Scale

	Skin Irritation Rating Scale Reactive area(s) within the treatment site only				
Condition	Rating	Description			
	0	No reaction			
Em the area	1	Mild and/or transient redness			
Erythema	2	Moderate redness			
	3 ^a	Severe redness			
	0	No reaction			
Edomos	1	Mild and/or transient swelling			
Edema	2	Moderate swelling			
	3ª	Severe swelling			
	0	No reaction			
Rash	1	Mild and/or transient rash			
Rasn	2	Moderate rash			
	3ª	Severe rash			
	0	No reaction			
Drugge	1	Mild and/or transient dryness			
Dryness	2	Moderate dryness			
	3ª	Severe dryness			

^a = A rating of 3 on the skin irritation scale in any category will be recorded as Adverse Event and will require subject's removal from the study.

Page 53 of 53 Zurex Pharma, Inc. Project: ZX-ZP-0092 Microbac Protocol: 865.1.03.25.18

Microbac Project: 865-107

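### The only formal irritation test cuts the 0–3 scale at any score above zero, so a product difference in moderate (grade 2) reactions with similar overall rates is neither tested nor tabulated by product

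*Combined protocol and SAP*

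**What the plan says.** Section 7.1 gives irritation its standing: "The principal measures of safety will be the recording of skin irritation scores and the incidence of adverse events reported during the study". Section 7.2 sets the level of detail: "A corresponding rating score for each individual skin condition, for each site will be recorded". Appendix 14.11 grades erythema, edema, rash and dryness each from 0 to 3. For erythema, grade 1 is "Mild and/or transient redness"; grades 2 and 3 are moderate and severe.

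Section 8.2.2 then plans four outputs that touch irritation:

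- **A formal test.** "The statistical significance of differences in skin irritation between the three treatments will be evaluated using Fisher's exact test". Its input is binary for each product: "any reaction above zero (no reaction) on the skin irritation rating scale for any category (erythema, edema, rash, and dryness"), at any post-treatment sampling time. No significance level is stated.
- **A conditional follow-up.** If the test is significant, "a secondary analysis will be conducted to determine how the reactions differ". No method is given.
- **Subject-level reporting.** "Skin irritation scores assessed in accordance with Appendix 14.11 will be reported for any subject who is scored with a 1 or more". This covers every observation, category and site.
- **Adverse events.** "Adverse events (including post-treatment skin irritation scores of 3 in accordance with Appendix 14.11, will be summarized", with incidence rates by treatment group and listings.

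Section 3.6.2 makes a post-treatment 3 a reason for discontinuation and says that a 2 may be one, at the investigator's discretion. Section 8.4 provides a summary and/or listing of reasons for discontinuation.

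**The concern.** The grades are recorded because they carry different weight, and the protocol's own rules treat 1, 2 and 3 differently. The formal test gives all three the same weight. If one product causes mostly passing redness and another causes moderate reactions about as often, the test has nothing to detect, because its null hypothesis is true. The follow-up that might show the difference is then not run.

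The other outputs do not fill the gap for grade 2. Adverse event rates expressly take in irritation scores of 3, and nothing makes a 2 an adverse event automatically. Subject-level reporting gives no rate by product, and each subject receives two products. Reasons for discontinuation capture a 2 only if the investigator stops that subject.

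At stake is whether the report can say anything organised about moderate irritation by product. Conversely, a significant result could reflect grade 1 alone. No efficacy criterion depends on irritation.

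**Working it through.** **No figure to reproduce.** The documents give no expected rate, power or significance level for the irritation test. All rates and the 0.05 level below are assumptions.

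**Inputs from the documents.** At least 108 subjects (section 1.5), each receiving two of three treatments (section 3.1): 108 × 2 / 3 = 72 per treatment, which matches Table 1.5. Safety uses the ITT population, so the actual number may be somewhat larger.

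**Which output carries which grade, by product**

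| Worst post-treatment score | Formal test | Rate by product | Subject-level report |
|---|---|---|---|
| 1 | pooled with 2 and 3 | none planned for this grade | yes |
| 2 | pooled with 1 and 3 | none planned for this grade | yes |
| 3 | pooled with 1 and 2 | yes, as adverse event | yes |

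**A constructed example.** Scores 0/1/2/3 in 72 readings: product A 57/3/12/0; the other two 57/15/0/0 each.

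- Any score above zero: A has 3 + 12 = 15, the others 15 each. The three-group Fisher test on 15 v 15 v 15 gives p = 1.00.
- Score of 2 or more: 12 v 0 v 0. The three equally extreme tables give p = 3 × C(72,12) / C(216,12) = 0.000003.

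**Power of pairwise comparisons.** For true rates p₁ and p₂, power = Σₐ Σᵦ Bin(a; 72, p₁) × Bin(b; 72, p₂) over all pairs (a, b) whose two-sided Fisher p-value is at most 0.05. Pairing within subject is ignored.

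*Similar overall rates, different severity:*

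| Comparison | Assumed rates | Significant |
|---|---|---|
| Any score above zero (planned) | 20% v 20% | 3.2% |
| Any score above zero (planned) | 40% v 40% or 60% v 60% | 3.4% |
| Any score above zero (planned) | 50% v 40% | 19% |
| Score of 2 or more | 15% v 1% | 87% |
| Score of 2 or more | 10% v 1% | 54% |
| Score of 2 or more | 5% v 1% | 8% |

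*All grades rise together, 20% of reactions graded 2 or more in both products:*

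| Any reaction | Planned test | Score of 2 or more | Power at 2 or more |
|---|---|---|---|
| 30% v 10% | 83% | 0.20 × 30% = 6% v 0.20 × 10% = 2% | 9% |
| 40% v 15% | 90% | 0.20 × 40% = 8% v 0.20 × 15% = 3% | 13% |

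With rare grade 2 events the threshold is demanding: 5 v 0 gives p = 0.058 and 6 v 0 gives p = 0.028.

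**Would a rank test on the grades do instead?** Three-arm simulation, 800 runs per scenario, equal any-reaction rates of 10%, 20% and 30%. In product A, 50% of reactions are grade 2 and 10% grade 3; in the others all are grade 1. Kruskal–Wallis rejects in 4.8%, 4.8% and 9.4% of runs, the planned test in 4.3%, 3.4% and 4.1%, and the comparison at 2 or more in 62.5%, 97.8% and 100%. The many zeros swamp the ranks, so an ordinal test does not by itself close the gap.

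**The case against.** The strongest reply is that any sign above zero is the most sensitive cut when reactions are few, and that a more irritating product usually raises all grades together. The proportional scenarios support this: the planned test wins clearly there. It is also true that equal any-reaction rates make the planned test's null hypothesis true, so rejecting in about 3% of trials is its correct size. It measures what the test does not look at; it is not a defect in how the test works. Moreover, the information is not lost: scores are recorded by sign and site, and products are assigned by side, so someone could count grade 2 reactions by product from the reported data.

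All of this stands, and it is why the planned test should remain the formal one. It does not supply a planned grade 2 summary.

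A reader might infer three stronger things that the documents do not support:

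- *That section 8.2.2 contains no other product comparison.* It also plans adverse event rates by treatment group and the conditional follow-up. The Fisher test is the only prespecified significance test of irritation.
- *That severe reactions are hidden.* Every post-treatment 3 is an adverse event and enters those rates and the listings.
- *That a non-significant result will be reported as no difference.* No section says so, and non-significance would not show it.

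**Conclusion.** The point holds for grade 2. A product difference in moderate reactions, with similar any-reaction rates, would be neither tested nor tabulated by product, and the conditional follow-up would ordinarily not be triggered. On the assumed rates (72 per product, two-sided 0.05, pairing ignored), such a difference is flagged about 3% of the time when grade 2 occurs in 15% versus 1%, against 87% for a comparison at 2 or more.

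The masking is conditional. If the product with more moderate reactions also has a clearly higher overall rate, the planned test can detect it and the follow-up is run. Nothing in the documents shows which pattern to expect. This is an inexpensive gap in planned safety reporting; it does not invalidate the Fisher test and does not touch the efficacy criteria.

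**What to change.** In section 8.2.2, keep the any-above-zero Fisher test as the formal test and add:

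1. A table by product and body area of the worst post-treatment score (0, 1, 2, 3) for each of the four signs, at 30 seconds and at 6 hours, produced whatever the Fisher result.
2. A supplementary estimate of the product differences in the proportion with a worst post-treatment score of 2 or more, with 95% confidence intervals, using the same unit of analysis as the any-above-zero comparison.

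Label the second item as supplementary to the formal test.

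The cost is SAP wording, one table and one set of estimates on data already collected. No assessment or discontinuation rule changes. The downside is one more safety comparison, which will be imprecise if moderate reactions are rare (about 8% power at an assumed 5% versus 1%). In that case the table and the width of the interval are the useful output.
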